The Multidisciplinary Association for Psychedelic Studies (MAPS) is a non-profit research and educational organization working as a clinical trial sponsor to obtain approval for the prescription use of 3,4-methylenedioxymethamphetamine (MDMA) as an adjunct to psychotherapy in patients with posttraumatic stress disorder (PTSD). Data from a series of Phase 2 studies of MDMAassisted psychotherapy conducted by the sponsor provide preliminary evidence that chronic PTSD, independent of cause, is treatable with two to three sessions of MDMA-assisted psychotherapy and associated non-drug preparatory and integrative psychotherapy. This openlabel Phase 2 study will serve as the lead-in to the sponsor's two planned Phase 3 studies, only sites planned for Phase 3 will participate in this study. This open-label lead-in Phase 2 study will serve to validate assumptions made for statistical power calculations supporting planned Phase 3 clinical trials and will provide data on the updated version of the instrument for the Primary Outcome measure, the Clinician Administered PTSD Scale for DSM-5 (CAPS-5), which will be used in Phase 3. In addition, the study will gather supportive data on the safety and effect of manualized MDMA-assisted psychotherapy while providing an opportunity for clinical supervision to planned Phase 3 therapy teams. This study will be the sponsor's first multi-site study of MDMA-assisted psychotherapy for PTSD and will explore reproducibility of findings in a multi-site format to confirm the Phase 3 study design.

PTSD is a serious debilitating disorder that negatively impacts a person's daily life, and can result in diminished cognitive and psychosocial functioning, fractured relationships, inability to maintain employment, substance abuse, high-cost healthcare utilization, increased depression, and suicide risk. People who suffer from PTSD relive their traumatic experience(s) through nightmares and flashbacks, have difficulty sleeping, and feel detached or estranged. Symptoms can be severe and long lasting. MDMA is a monoamine releaser and re-uptake inhibitor with indirect effects on neurohormone release. The combined neurobiological effects reduce defenses and fear of emotional injury, enhance communication and introspection, and can increase empathy and compassion. MDMA may enhance fear extinction learning in humans. The subjective effects of MDMA create a productive psychological state that enhances the therapeutic process.

Study Design

This multi-site, open-label lead-in study assesses the safety and effect of MDMA-assisted psychotherapy in participants diagnosed with at least severe PTSD. All data will be included in the sponsor's safety database. Therapy teams that have been identified to work on the sponsor's planned Phase 3 studies will treat at least one open-label participant in this study. The study will be conducted in up to N=60 participants.

A flexible dose of MDMA, followed by a supplemental half-dose unless contraindicated, is administered during the Treatment Period with manualized psychotherapy in three open-label monthly Experimental Sessions. This ~12-week Treatment Period is preceded by three Preparatory Sessions. During the Treatment Period, each Experimental Session is followed by three Integrative Sessions of non-drug psychotherapy. Experimental Sessions are followed by an overnight stay; a sub-study (Appendix A) will assess feasibility of Experimental Sessions without an overnight stay. The Primary Outcome measure, the change in CAPS-5 from Baseline (V3), is assessed by a centralized Independent Rater (IR) pool at 18 weeks post Baseline (V19). The CAPS-5 is also administered as an exploratory measure after Treatments 1 and 2 (V8 and V13). The IR pool will be blinded to visit number and number of treatments received and will not have access to data collected by the sites during the active treatment period.

For each participant, the study will consist of:

- **Screening Period**: phone screen, informed consent, eligibility assessment, and enrollment of eligible participants
- **Preparatory Period with Enrollment Confirmation**: medication tapering, Preparatory Sessions and Baseline assessments leading to Enrollment Confirmation
- **Treatment Period**: three monthly Experimental Sessions and associated Integrative Sessions over ~12 weeks plus two CAPS-5 assessments
- Follow-up Period and Study Termination: 4 weeks with no study visits, followed by Primary Outcome CAPS-5 and Study Termination visit
- Invitation to participate in Long-term Follow-up (LTFU) extension study: 12 months after last Experimental Session.

Study Design Overview

	Screening Period			
From Consent to Enrollment (Visit 0): ~4 weeks (+/-2 weeks) Study Visit				
Stuc	ly visit	Visit Duration/ Visit Timing/	Brief Description of Events	
		(Scheduling Window)		
Screening Multip weeks After		Multiple visits over 3 weeks/ After phone screen/ (-2 weeks/+1 week)	At initial visit, obtain Informed Consent and assess all screening measures (including PCL-5, Lifetime C-SSRS), medical history, and pre-study medications. Contact outside providers and order medical records, physical exam, labs (including pregnancy and drug tests), ECG, and 1-minute rhythm strip. Once all results and records are obtained, review along with notes from all screening visits and measures. If eligible, send results of LEC-5 & SCID-5-SPQ to IR. Screening may take place over 3 weeks at multiple visits.	
	Independent Rater Screening	1 hour/ 2 days after initial eligibility established during Screening/ (+7 days)	After PCL-5 and initial eligibility are reviewed, an IR will conduct the Since Last Visit C-SSRS, SCID-5-PD, DDIS, and MINI via telemedicine. Results will be confirmed by clinical observation during the Preparatory Period, but the SCID-5-PD, DDIS, and MINI will not be repeated.	
Enrollment	Enrollment (Visit 0)	1.5 hours/ 2 days after Independent Rater Screening (+12 days)	Prior to enrolling: review all screening measures, medical history, discussion with outside providers and sponsor, and any clarification phone calls with participant. Visit is 1.5 hours to review eligibility and medical tapering plan. If enrolled, begin taper, (5 half-lives plus 1 week for stabilization). Adverse Event (AE) collection begins.	

	Preparatory Period with Enrollment Confirmation			
From Preparatory Session 1 (Visit 1) to Preparatory				
Study Visit #		Visit Duration/ Visit Timing/	Brief Description of Events	
V ISIL T	•	(Scheduling Window)		
riod	Preparatory Session 1 (Visit 1)	1.5 hours/ Within 1 week (0 to 12 days) of Enrollment (V0)	90-minute Preparatory Session. Target visit timing on tapering needs. If needed, schedule calls between V1 and V2 if indicated for tapering, safety, or further questions about medical history.	
Preparatory Period	Preparatory Session 2 (Visit 2)	1.5 hours/ Within 3 weeks of V1	90-minute Preparatory Session/ongoing assessment. If tapering is complete or not needed, check eligibility and schedule V3 and V4. If tapering is ongoing, schedule post taper call for ongoing assessment.	
	Phone Call End Taper	1 hour/ Within 1 week of taper end & 8 weeks of V0	If needed, confirm medication taper and stabilization is complete and participant is eligible for Baseline CAPS-5. Schedule V3 and V4.	
ent	Baseline CAPS-5 T1 (Visit 3)	1.5 hours/ Post V2 & Medication Taper; before V4	CAPS-5, SDS, and DSP-I completed by an IR via telemedicine after taper is complete. CAPS scores sent ASAP to the therapy team/PI.	
Baseline & Enrollment Confirmation	Preparatory Session 3 & Enrollment Confirmation (Visit 4)	3 hours: (95 minutes of measures, 90 minute therapy) Within 6 days of V3	Prior to visit, ensure CAPS-5 confirms PTSD diagnosis and Total Severity Score of ≥35 and confirm enrollment by reassessing specified eligibility criteria. Complete Baseline self-report measures. Complete 3 hour Preparatory Session (~95-min measures, 90-min therapy) and schedule V5. If enrollment is not confirmed, do not perform visit; complete termination and put on waiting list for Expanded Access study if appropriate.	

Treatment Period From Experimental Session 1 (Visit 5) to Integrative Session 3.3 (Visit 18): 12 weeks (-3/+4)			
Study Visit/ Visit #		Visit Duration/ Visit Timing/ (Scheduling Window)	Brief Description of Events
	Experimental Session 1 (Visit 5)	8 hours + overnight/ Within 1 week of V3, at least 2 weeks after V2	First Experimental Session is within 1 week of the Baseline CAPS-5 (V3) and 2 weeks after Preparatory Session 2 (V2); it lasts 8 hours with overnight stay. Dose is 80 mg with supplemental half-dose of 40 mg unless contraindicated.
ıt 1	Integrative Session 1.1 (Visit 6)	1.5 hours/ Morning after V5	V6 is a 90-minute Integrative Session the morning after V5. Followed by 4 phone check-ins over the 7 days post V5.
Treatment 1	Integrative Session 1.2 (Visit 7)	1.5 hours/ within 2 weeks of V5	Approximately 2 weeks after V5, a 90-minute Integrative Session (V7) is completed.
	CAPS-5 T2 (Visit 8)	1 hour Within 3 weeks after V5 Complete before V9	Between V7 and V9, CAPS-5, SDS, and DSP-I assessment completed by an IR via telemedicine.
	Integrative Session 1.3 (Visit 9)	1.5 hours/ Within 4 weeks of V5 1-7 days before V10	90-minute Integrative Session post V8 and in preparation for V10. Can occur 1 to 7 days before V10. Measures include LEC-5, PCL-5, and C-SSRS.

Study Visit/ Visit #		Visit Duration/ Visit Timing/ (Scheduling Window)	Brief Description of Events
	Experimental Session 2 (Visit 10)	8 hours + overnight/ Within 4 weeks of V5/ (+/-1 weeks), at least 2 weeks after Visit 7	3 to 5 weeks after V5, and 2 weeks after Integrative Session 1.1 (V6). The second Experimental Session lasts 8 hours with an overnight stay. Dose is 80 or 120 mg plus supplemental half-dose unless contraindicated.
2	Integrative Session 2.1 (Visit 11)	1.5 hours/ Morning after V10	V11 is a 90-minute Integrative Session the morning after V10. Followed by 4 phone check-ins over 7 days post V10.
Treatment 2	Integrative Session 2.2 (Visit 12)	1.5 hours/ Within 2 weeks of V10	Approximately 2 weeks after V10, a 90-minute Integrative Session (V12) is completed.
Tr	CAPS-5 T3 (Visit 13)	1 hour/ Within 3 weeks after V10 Complete before V14	Between V12 and V14, CAPS-5, SDS, and DSP-I assessment completed by an IR via telemedicine.
	Integrative Session 2.3 (Visit 14)	1.5 hours/ Within 4 weeks of V10 1-7 days before V15	90-minute Integrative Session post V13 and in preparation for V15. Can occur up to 1 to 7 days before V15. Measures include LEC-5, PCL-5 and C-SSRS.
	Experimental Session 3 (Visit 15)	8 hours + overnight/ Within 4 weeks of V10 (+/-1 weeks), at least 2 weeks after Visit 12	3 to 5 weeks after V5, and 2 weeks after Integrative Session 2.1 (V11). The third Experimental Session lasts 8 hours with an overnight stay. Dose is 80 or 120 mg plus supplemental half-dose unless contraindicated.
Treatment 3	Integrative Session 3.1 (Visit 16)	1.5 hours/ Morning after V15	V16 is a 90-minute Integrative Session the morning after V15. Followed by 4 phone check-ins over 7 days post V15.
Tre	Integrative Session 3.2 (Visit 17)	1.5 hours/ Within 2 weeks of V15	Within 2 weeks after V15, a 90-minute Integrative Session (V12) is completed.
	Integrative Session 3.3 (Visit 18)	1.5 hours/ Within 4 weeks of V15	90-minute Integrative Session post V17, within 4 weeks of V15. Measures include LEC-5 and C-SSRS.

From After 1	Follow-up Period and Study Termination From Integrative Session 3.3 (Visit 18) until Study Termination (Visit 20): 4 weeks (+/-2). After Integrative Session 3.3 (Visit 18), ~4 weeks with no scheduled study visits until the Primary Outcome is completed.			
Study Visit #		Visit Duration/ Visit Timing/	Brief Description of Events	
V ISIL #	•	(Scheduling Window)		
Primary Outcome CAPS-5 T4 (Visit 19) Primary Outcome CAPS-5 T4 (Visit 19) 8 (+/-2) weeks post V15		~18 (+/-3) weeks post Baseline & 8 (+/-2) weeks post	Within 18 weeks (+/-3 weeks) of Baseline and 8 weeks (+/-2 weeks) after Experimental Session 3 (Visit 15), Primary Outcome CAPS-5, SDS, and DSP-I assessment completed by an IR via telemedicine. Although there are allowable windows for all visits throughout the protocol, this visit must be completed within the overall window. Other visits should be scheduled to ensure the timing of the Primary Outcome CAPS-5 T4 assessment is appropriate.	
Study Termination	Study Termination (Visit 20)	2 hours ~18 (+/-3) weeks post Baseline & 2 days post V19/ (-1/+7 days)	Occurs ~18 weeks post Baseline and within 1 to 9 days of V19. Complete self-reported and safety measures; create an exit plan for participant. Invite participant to the extension study for LTFU.	

Qualified IRs selected based on availability from the IR Pool will perform the CAPS-5 assessments as described in the following table.

Primary Outcome (CAPS-5) Data Collection by Visit

CAPS Number	Visit	Description/Timing	Target Timing Post Baseline (V3)
Baseline CAPS-5 T1	V3	Baseline	0 days
		Between V2 and V4 Preparatory Sessions	
CAPS-5 T2	V8	Post Experimental Session 1 (~3 weeks)	~6 weeks
		Between V7 and V9 Integrative Sessions	
CAPS-5 T3	V13	Post Experimental Session 2 (~3 weeks)	~10 weeks
		Between V12 and V14 Integrative Sessions	
Primary Outcome	V19	Post Experimental Session 3 (~8 weeks)	~18 weeks
CAPS-5 T4			

Dose Selection

This study will compare the effects of three open-label manualized Experimental Sessions of psychotherapy assisted by flexible doses of MDMA as described in the table below, along with associated non-drug preparatory and integrative psychotherapy. Similar MDMA doses to those proposed in this study have been safely used in previous Phase 2 studies sponsored by MAPS.

Dose Regimen of MDMA

Experimental Session	Initial Dose	Supplemental Dose*	Min-Max Cumulative Dose
1	80 mg	40 mg	80 mg to 120 mg
2	80 or 120 mg	40 or 60 mg	80 mg to 180 mg
3	80 or 120 mg	40 or 60 mg	80 mg to 180 mg
	r	Fotal Cumulative Dose	240 mg to 480 mg

^{*} Unless contraindicated

Protocol Objective

The overall objective of this study is to use standard clinical measures to explore the safety and effects of open-label manualized MDMA-assisted psychotherapy with a flexible dose of MDMA in participants with severe PTSD and to serve as an opportunity for supervision of therapy teams selected to conduct Phase 3 MDMA-assisted psychotherapy research.

Primary Objective

The primary objective of this study is to evaluate the effect of MDMA-assisted psychotherapy on PTSD, as measured by the estimand of change in CAPS-5 Total Severity Score from Baseline (Visit 3) to 18 weeks post Baseline (Visit 19).

Secondary Objective

The secondary objective is to evaluate the effect of MDMA-assisted psychotherapy for PTSD in clinician-rated functional impairment, as measured by the mean change in Sheehan Disability Scale (SDS) item scores from Visit 3 (Baseline) to Visit 19 (18 weeks post Baseline).

Safety Objectives

The overall safety objective is to assess severity, incidence and frequency of AEs, AEs of Special Interest (AESIs), and Serious Adverse Events (SAEs), concomitant medication use, suicidal ideation and behavior, and vital signs to support the package insert for MDMA-assisted psychotherapy. The following safety objectives will evaluate the safety of MDMA-assisted psychotherapy.

- 1. Assess incidence of AEs during Experimental Sessions that may be indicative of a medical complication of the Investigational Product (IP), such as clinical signs and symptoms of chest pain, shortness of breath, or neurological symptoms or any other signs or symptoms that prompt additional vital sign measurements.
- 2. Assess incidence of AEs by severity.
- 3. Assess incidence of Treatment Emergent AEs (TEAEs) by severity.
- 4. Assess incidence of TEAEs by severity taken during an Experimental Session and 2 days after IP administration.
- 5. Assess incidence of AESIs, defined as AEs specified in the protocol related to cardiac function and abuse liability.
- 6. Assess incidence of AEs by severity categorized as leading to discontinuation of IP, resulting in death or hospitalization, and continuing at Study Termination.
- 7. Assess incidence of SAEs.
- 8. Assess incidence of psychiatric concomitant medications taken during an Experimental Session and 2 days after IP administration.
- 9. Assess incidence of any psychiatric concomitant medications taken during the Treatment Period
- 10. Assess incidence of serious suicidal ideation and positive suicidal behavior assessed with the Columbia Suicide Severity Rating Scale (C-SSRS).
- 11. Assess mean changes in blood pressure, heart rate, and body temperature from pre-IP administration to end of each Experimental Session.

Recruitment and Participant Population

Therapy teams that have been identified to work on the sponsor's planned Phase 3 studies will treat at least one open-label participant in this study. Up to N=60 participants with a confirmed diagnosis of at least severe PTSD will be enrolled. Participants will be recruited through print and internet advertisements, referrals from other psychiatrists, psychotherapists, or physicians, and by

[figure not shown]
word of mouth. The sponsor will monitor demographics on an ongoing basis and encourage diversity in enrollment by communicating with sites.

Participants will be persons aged 18 or older, with a confirmed diagnosis of at least severe PTSD per the PCL-5 at Screening with symptoms present for at least 6 months. At Baseline, participants must qualify for a PTSD diagnosis per the CAPS-5 and have a Total Severity Score equal to or greater than 35 (severe). Participants would not be excluded for having more than one traumatic event or for having tried, not tolerated, or refused a selective serotonin reuptake inhibitor (SSRI) or serotonin norepinephrine reuptake inhibitor (SNRI) prescribed for PTSD. Participants with confirmed diagnosis of specific psychological and personality disorders will be excluded. Participants must be in good physical health and without major medical disorders that could affect the safety or tolerability of MDMA.

Statistical Analysis

All outcome analyses will be based on the *m*ITT analysis set. Change from Visit 3 (Baseline) in CAPS-5 Total Severity Scores to Visit 19 (Primary Outcome) will be analyzed with least squares means from a Mixed-Effect Repeated Measures model (MMRM). The *m*ITT analysis set will include all participants who receive IP in at least one Experimental Session and have at least one follow-up CAPS-5 assessment.

Study Structure Overview

MP16 Protocol IND #063384

Original Protocol Version 1: 18 May 2017 Amendment 1 Version 1: 03 January 2018

An Open-Label, Multi-Site Phase 2 Study of the Safety and Effect of Manualized MDMA-Assisted Psychotherapy for the Treatment of Severe Posttraumatic Stress Disorder

SPONSOR Multidisciplinary Association for Psychedelic Studies (MAPS)

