Enrollment		Independent Rater	and sponsor, and any clarification phone calls with	
rol		Screening (±12 days)	participant. Visit is 1.5 hours to review eligibility	
En		(+12 days)	and medical tapering plan. If enrolled, begin taper, (5 half-lives plus 1 week for stabilization). Adverse	
			Event (AE) collection begins.	
			Event (AE) conection begins.	

Preparatory Period with Enrollment Confirmation				
From Preparatory Session 1 (Visit 1) to Preparatory Session 3 (Visit 4): ~6 weeks (+5/-4 weeks)				
		Visit Duration/	Brief Description of Events	
Visit #		Visit Timing/		
		(Scheduling Window)		
			90-minute Preparatory Session. Target visit timing	
	Session 1	Within 1 week (0 to 12	on tapering needs. If needed, schedule calls between	
_	(Visit 1)	days) of Enrollment	V1 and V2 if indicated for tapering, safety, or further	
Preparatory Period		(V0)	questions about medical history.	
Pe	Preparatory	1.5 hours/	90-minute Preparatory Session/ongoing assessment.	
ory	Session 2	Within 3 weeks of V1	If tapering is complete or not needed, check	
arat	(Visit 2)		eligibility and schedule V3 and V4. If tapering is	
ep?			ongoing, schedule post taper call for ongoing	
Pı			assessment.	
	Phone Call	1 hour/	If needed, confirm medication taper and stabilization	
	End Taper	Within 1 week of taper	is complete and participant is eligible for Baseline	
	D1:	end & 8 weeks of V0	CAPS-5. Schedule V3 and V4.	
	Baseline CAPS-5 T1	1.5 hours/ Post V2 & Medication	CAPS-5, SDS, and DSP-I completed by an IR via telemedicine after taper is complete. CAPS scores	
nt	(Visit 3)	Taper; before V4	sent ASAP to the therapy team/PI.	
me	Preparatory	3 hours: (95 minutes of	Prior to visit, ensure CAPS-5 confirms PTSD	
roll	Session 3	measures, 90 minute	diagnosis and Total Severity Score of ≥35 and	
En	& Enrollment	therapy)	confirm enrollment by reassessing specified	
Baseline & Enrollment Confirmation	Confirmation	Within 6 days of V3	eligibility criteria. Complete Baseline self-report	
	(Visit 4)		measures. Complete 3 hour Preparatory Session	
			(~95-min measures, 90-min therapy) and schedule	
B			V5. If enrollment is not confirmed, do not perform	
			visit; complete termination and put on waiting list	
			for Expanded Access study if appropriate.	

Treatment Period				
From Experimental Session 1 (Visit 5) to Integrative Session 3.3 (Visit 18): 12 weeks (-3/+4) Study Visit/ Visit Duration/ Brief Description of Events				

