5.3.3 Pre-Dosing Early Terminations

'Pre-Dosing Early Terminations' are defined as participants who were deemed eligible and enrolled in the study at Visit 0, but are deemed ineligible prior to the first Experimental Session and do not have enrollment confirmed at Visit 4. These participants may fail to meet all Inclusion Criteria and may meet one or more Exclusion Criteria or withdraw consent prior to Enrollment Confirmation or the site may withdraw the participant for reasons described in Section 5.3.4 Early Termination from the Study). Participants who fail Enrollment Confirmation may not be reenrolled into this study at a later date. All enrolled participants, even those failing Enrollment Confirmation, will be maintained in the EDC system. Pre-Dosing Early Terminations are not considered evaluable.

Pre-Dosing Early Terminations may be identified through review of medical history, assessments, measures, laboratory results, or conversations with the participant. At any time during the Preparatory Period, if a potential participant is deemed to be ineligible, classify as a Pre-Dosing Early Termination, notify the potential participant that they are not eligible for the study, and do not schedule additional assessments. Do not perform the next visit. Pre-Dosing Early Terminations will be provided an Exit Plan as described in Section 8.4.3.2 Exit Plan.

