7.3 Safety Measures

C-SSRS (Columbia Suicide Severity Rating Scale)

The C-SSRS is a clinician-administered measure of suicidal behavior devised to detect potential suicidal thoughts or behaviors during a clinical trial [65]. It consists of a Lifetime version and a Since Last Visit version that assess suicidal ideation, ideation intensity, and behavior. The C-SSRS consists of a series of questions, and can be administered during a face-to-face interview or over the telephone. The Lifetime version will only be administered at the initial Screening visit. All subsequent administrations will utilize the Since Last Visit version. Participants who are discontinuing medications to participate in the study will complete the C-SSRS before and after medication washout. The C-SSRS Intensity scale for Lifetime obtained a Cronbach's alpha of 0.93 and 0.94 for the Since Last Visit form, and Last Visit C-SSRS severity scores were positively correlated with the BDI "suicide thoughts" item [66].

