8.2 Preparatory Period with Enrollment Confirmation

Participants will undergo three Preparatory Sessions (Visits 1, 2, and 4) lasting approximately 90 minutes with the therapy team prior to the first Experimental Session. The Preparatory Period will be initiated within 12 days of Visit 0 and last one to 11 weeks, depending on duration of medication tapering. There must be at least 48 hours between Preparatory Sessions. The minimum time to complete the Preparatory Period is 2 weeks. The Preparatory Period will also include the Baseline CAPS-5 assessment (Visit 3), which will be assessed by an IR. Adherence criteria for Preparatory Sessions should be followed per the Treatment Manual. In these visits, the therapy team will work with the participant to prepare for MDMA-assisted psychotherapy, begin building therapeutic alliance, and promote a safe set and setting for confronting trauma-related memories, emotions, and thoughts.

8.2.1 Preparatory Sessions 1 and 2

Preparatory Sessions during the Preparatory Period will focus on psychoeducation about PTSD, building safety for the therapeutic relationship, developing the therapeutic alliance, obtaining the background for the trauma, and preparing the participant for the first Experimental Session. Telephone calls may be scheduled between visits if indicated for tapering, safety, or any further questions about medical history.

- Preparatory Session 1 (Visit 1) will occur within 1 week (0 to 12 days) of Visit 0. The visit timing should take in to account appropriate times for monitoring medication tapering.
- Preparatory Session 2 (Visit 2) will occur within 3 weeks of Visit 0 and at least 2 days after Visit 1. The visit timing should take into account appropriate times for monitoring medication tapering. Visit 2 must take place at least 2 weeks prior to Experimental Session 1 (Visit 5).

• If tapering is ongoing at Preparatory Session 2 (Visit 2), the site team will schedule a telephone phone call after tapering and stabilization are complete to confirm that the participant is eligible for the Baseline CAPS-5 assessment. If tapering is complete or not needed, the site team will confirm eligibility and schedule Baseline CAPS-5 T1 (Visit 3) and Preparatory Session 3 (Visit 4) as soon as possible.

At each 90-minute psychoeducation and psychotherapy Preparatory Session, the therapy team will:

- Record the therapy session.

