- Inquire about any possible changes in health to ensure the participant continues to meet all eligibility requirements. Record AEs as described in Section 11.0 Safety.
- Inquire about concomitant medication use and adherence.
- Confirm that medication tapering is ongoing or complete, as appropriate.
- Discuss goals and expectations for the Experimental Session, following standard procedures and techniques described in the Treatment Manual [108].

If a participant would like a companion present during or after the Experimental Session, a meeting between the therapy team and that individual will be scheduled prior to the first Experimental Session. There must be mutual agreement between the participant and therapy team concerning the presence of the companion.

During one of the Preparatory Sessions, if possible, the therapy team will introduce the participant to the attendant who will remain with the participant during each overnight stay after each MDMA-assisted psychotherapy session. The attendant will be an individual with previous training in managing psychological distress. The site will make all attempts to have the same attendant for each Experimental Session for a given participant, but it is not guaranteed.

At any time during the Preparatory Period, if a potential participant is deemed to be ineligible, the site team will classify them as an Enrollment Confirmation Failure, notify the potential participant that they are unfortunately not eligible for the study, and not schedule additional assessments. If appropriate, the site team will place the participant on a waiting list for an Expanded Access study.

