8.4.3 Study Termination

Study Termination (Visit 20) will take place 2 (-1/+7) days after the final CAPS-5 assessment (Visit 19). Participants who have withdrawn from treatment but have continued for follow-up will also complete this assessment immediately upon withdrawal.

The site team will:

- Inquire about any possible changes in health. Assess the participant's mental health and the status of any previously recorded AEs. Record AEs as described in Section 11.0 Safety.
- Inquire about concomitant medication use and adherence.
- Administer Since Last Visit C-SSRS.
- Measure weight (used to calculate BMI).
- Measure blood pressure.
- Provide and discuss a study exit plan.
- Ask them to enroll into the LTFU extension study with a visit at 12 months after the last experimental session. Review contact information and Informed Consent procedures for LTFU
- Actively support participant in completion of Study Termination self-reported measures:
 - o LEC-5
 - o PCL-5- ensure assessment is in relation to index trauma
 - o BDI-II
 - CPGS
 - o EQ-5D-5L
 - o IASC
 - o IPF
 - o SCS
 - o TAS-20
 - o AUDIT
 - o DUDIT
 - o SRNU
 - EAT-26
 - HPQSF

Completion of the measures do not need to be recorded.

After all Study Termination measures and assessments are completed, the participant is considered terminated from the study. The participant can resume normal everyday life. The study team will provide an Exit Plan, which may include a referral for additional medical or therapeutic care, as described in Section 8.4.3.2 Exit Plan. Eligible participants will be asked to participate in the LTFU extension study, described in Section 8.4.3.1 Extension Studies.

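### A tapered participant found ineligible before Visit 4 can leave the study without the post-washout C-SSRS that protocol Section 7.3 requires

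*Protocol*

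**What the plan says.** Section 7.3 of the protocol makes an unconditional commitment: "Participants who are discontinuing medications to participate in the study will complete the C-SSRS before and after medication washout". It has no exception for people who later fail Enrollment Confirmation.

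The taper begins at Visit 0 (Synopsis table and Table 1). The contacts that follow are described without a C-SSRS:

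- **Visits 1 and 2** (Section 8.2.1): therapy, a check on health, medication and eligibility. Table 6 has no column for either visit.
- **End-of-taper call**, made when tapering is still under way at Visit 2: "the site team will schedule a telephone phone call after tapering and stabilization are complete". The Synopsis table gives its content: "If needed, confirm medication taper and stabilization is complete and participant is eligible for Baseline CAPS-5. Schedule V3 and V4".
- **Visit 3** (Section 8.2.2): CAPS-5, SDS and DSP-I by an independent rater. The C-SSRS cell in Table 6 is empty.
- **Visit 4** (Section 8.2.3 and Table 6): C-SSRS scheduled, among the procedures for eligible participants.

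For someone who fails before Visit 4, the Synopsis table states: "If enrollment is not confirmed, do not perform visit; complete termination and put on waiting list for Expanded Access study if appropriate". Table 1 repeats this. Section 5.3.3 adds, for Pre-Dosing Early Terminations, "do not schedule additional assessments. Do not perform the next visit", and provides an Exit Plan. Section 8.2.1 tells the site to "notify the potential participant that they are unfortunately not eligible for the study, and not schedule additional assessments".

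**The concern.** The only scheduled form that can meet the post-washout half of Section 7.3 sits at a visit that is cancelled for exactly those participants who fail just before it. Failing Enrollment Confirmation is an outcome the design provides for, because inclusion criterion 13 is first tested at Visit 3, after washout.

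These people entered with a PCL-5 of 50 or more, a history of suicide attempts does not exclude them, and their psychiatric drugs were stopped for the trial. The management plan in Section 10.1.2 is triggered by C-SSRS scores, so without a form its stated trigger is absent. A site that follows the schedule literally can discharge a newly unmedicated participant with severe PTSD at entry without the structured check the protocol promises.

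The group is limited. It excludes people found ineligible during Visit 4 and people who fail before washout ends.

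**Working it through.** The plan gives no figure to reproduce. The check traces every scheduled C-SSRS against the taper timeline.

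**1. Forms before washout.** Lifetime version at site Screening; Since Last Visit version at IR Screening (Section 8.1.2). Both precede Visit 0. The pre-washout half of Section 7.3 is met.

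**2. Contacts after washout and before Visit 4.**

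| Path | Contacts | Scheduled C-SSRS |
|---|---|---|
| Taper ongoing at Visit 2 | End-of-taper call, Visit 3 | 0 of 2 |
| Washout complete by Visit 2 | Visit 2, Visit 3 | 0 of 2 |

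**3. Cross-check on the Table 6 minutes.**

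- Visit 3: CAPS-5 90 + SDS 2 + DSP-I 15 = 107, the stated total. No C-SSRS is included.
- Visit 4: C-SSRS 10 + PCL-5 8 + ACE 4 + BDI-II 10 + CPGS 5 + EQ-5D-5L 3 + IASC 15 + IPF 10 + SCS 6 + TAS-20 5 + SRNU 3 + EAT-26 6 + HPQSF 5 + UFEC 3 = 93, the stated total. The C-SSRS is included.

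The empty cell at Visit 3 and the tick at Visit 4 are therefore not artefacts of the table layout.

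**4. Forms between end of washout and exit.**

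- Tapered participant who attends Visit 4 as eligible: 1.
- Tapered participant found ineligible after washout and before Visit 4: 0, against at least 1 required by Section 7.3.

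**5. Could the termination wording supply the form?** The Synopsis row says to complete termination, and the Visit 20 procedures include a C-SSRS. Section 8.4.3, however, extends an early Visit 20 to a different group: "Participants who have withdrawn from treatment but have continued for follow-up will also complete this assessment immediately upon withdrawal". A person never dosed has not withdrawn from treatment with continued follow-up. Section 5.3.3 gives this group an Exit Plan, and the contents listed in Section 8.4.3.2 include no suicidality assessment.

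**6. Interval since the last scheduled form.**

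- IR Screening to Visit 0: 2 days, window +12, so 2 to 14 days (Section 8.1.3).
- Preparatory Period from enrollment: 2 to 11 weeks, so 14 to 77 days (Section 5.2).
- IR Screening to Visit 4: 2 + 14 = 16 days to 14 + 77 = 91 days.
- If the 2 to 11 weeks runs from Visit 1, as in Table 1, and Visit 1 is up to 12 days after Visit 0, the maximum is 14 + 12 + 77 = 103 days.

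These intervals run to the planned Visit 4, which the affected participant does not attend. The documents do not time the exit contact, so the figures indicate the length of the gap and do not measure it exactly.

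**The case against.** The strongest reply is that Section 7.3 is itself binding. A site following the whole protocol owes the form, and the instructions against scheduling further assessments need not cancel one already due. On this view the defect is a missing table entry. Nothing forbids giving the form at the end-of-taper call, and Section 10.1.2 allows it as needed. This stands as a description, but the schedule names no contact for the form, and the rules for ineligible participants point the other way. As-needed use depends on clinical presentation.

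Second, there is other cover. Exclusion criterion 12, which draws on C-SSRS responses, is reassessed after Screening, and eligibility is rechecked at Visit 2 and at the end-of-taper call. AEs are collected from Visit 0, and participants are asked how they feel at each contact. The prescribing physician is consulted on the taper, a contact person is named, and a referral is available on request. All this lowers the risk, but none of it guarantees a completed form. The Section 8.1.2 instruction that the rater alert the therapy team to suicidal ideation is not repeated for Visit 3 in Section 8.2.2.

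Third, the group is narrow and uncounted. Someone excluded for a CAPS-5 below 35 has just rated below severe, and would have reached Visit 4 within 6 days of Visit 3. That is fair and limits the weight of the point.

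Fourth, a form at exit alone would close the gap, and SAP Table 3 reproduces Table 6, so it would need the same footnote. Both points are correct, and both bear on the remedy rather than on whether the gap exists.

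**Conclusion.** The concern holds. For a tapered participant found ineligible after washout and before Visit 4, the schedule delivers 0 post-washout C-SSRS forms where Section 7.3 requires one. The planned Visit 4 falls 16 to 91 days after the last scheduled form, or up to 103 days on the Table 1 count.

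This rests on two readings: that the termination instruction in the Synopsis table does not mean Visit 20 for undosed participants, and that an as-needed provision does not satisfy an unconditional requirement. If the sponsor did intend Visit 20, the text still needs to say so.

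The number affected is not given in the documents and is not estimated here. The mITT analysis is unaffected, and undosed participants are also outside the Safety set. This is a safety-monitoring gap that should be closed; it does not threaten the trial's results.

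**What to change.** Schedule one Since Last Visit C-SSRS for every tapered participant once washout and stabilization are complete and before Visit 3. Site staff give it at the end-of-taper call, or at Visit 2 if washout and stabilization are already complete by then. Visit 3 is less suitable: adding 10 minutes to its 107 gives 117, against a slot of 1.5 hours (90 minutes).

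As a back-up, require the form at the termination or Exit Plan contact for any Pre-Dosing Early Termination who has completed washout and has neither this form nor a Visit 4 form. Section 7.3 allows telephone administration, and Table 6 footnote C already schedules the C-SSRS at calls. If the sponsor wants the smallest change, the back-up alone closes the gap, but it checks people only as they leave.

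**Cost.** Wording in six protocol places: the Synopsis table (end-of-taper and Visit 4 rows), Table 1, Table 6, and Sections 5.3.3, 8.2.1 and 8.4.3.2. SAP Table 3 should carry the matching footnote. No analysis text needs to change, because SAP Section 8.0 already sends unanalysed data to the listings. The time is about 10 minutes per tapered participant (the Table 6 allowance for the C-SSRS), at a contact that already exists; the end-of-taper call is allotted 1 hour. With the exit form alone, it is about 10 minutes per affected participant.
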